Objective #4: Each subject will undergo a detailed neuropsychological battery to characterize his or her cognitive and behavioral status—including targeted tests that should be affected by improved verbal retrieval, tests of cognitive functions to which the treatment may generalize, and tests consisting of purportedly unrelated functions to account for global, generalized cognitive improvement. They will also undergo pre-treatment EEG (SORT task with EEG, Semantic Selection task with EEG). These will be used as outcome measures for the treatment trial. The two primary outcome measures will be the COWAT and CVLT. Secondary outcome measures will be SORT and Semantic Selection task, performance and ERP for both sets of tasks.

Objective #5: These subjects will then be enrolled in the active treatment aspect of the study. Enrollment of 80 participants is the target for enrollment in the active phase of the treatment trial. Half the subjects will first receive HD tDCS at 1 mA for 20 minutes over the preSMA region for 10 daily sessions (1 session 5 days per week for a 2 week period). The remaining subjects will initially receive sham HD tDCS; after all follow-up evaluations are completed, they will receive the active HD tDCS treatment.

Objective #6: Each subject will receive follow-up neuropsychological and EEG testing at 1 week, 3 months, and 6 months after treatment. This last time point for evaluation extends from our preliminary work showing that later, further improvement in electromodulation treatments can occur at 6 months post-treatment. HD tDCS active treatment subjects enrolled early in the study will be followed longer than 6 months if agreeable to assess length of effect.

Following completion of this clinical trial, we will be able to determine whether HD tDCS is an effective treatment for the verbal retrieval deficits associated with GWI. An HD tDCS cap is a relatively inexpensive piece of equipment that can be re-used many times for multiple patient treatments. These caps are readily available, and the application of the treatment regimen is straightforward to administer. Thus, this treatment can be utilized in any VA medical center or clinic around the nation. In addition, the neuro-psychological tests and ERP/time frequency findings may function as clinical markers for diagnosis and treatment efficacy in subsequent treatment trials to measure treatment response.

SPECIFIC AIMS

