Hypothesis #2c: An increase in false negative errors and a decreased "Go"P3 ERP response on the Semantic Selection Tasks is indicative of an impaired ability to select a correct memory for retrieval.³³ Conversely, there will be increased false positive errors and a decreased "NoGo" P3 ERP on the Semantic Selection Tasks if a patient cannot inhibit an incorrect memory. *We hypothesize that following HD tDCS therapy, there will be a normalization of the patient's behavior (reduced errors, improved RTs) and/or ERP responses (increased P3 amplitudes for Go and/or NoGo trials) due to modulation of the retrieval circuit, with the changes based on the pre-treatment impaired retrieval function (selection and/or inhibition).*

CLINICAL TRIAL

A. General Experimental Approach.

1. We will screen 120 GWI patients who report subjective word-retrieval deficits over the phone with the COWAT.

2. A subject who on the phone screen has a subjective complaint and decrement in COWAT performance will then be consented and enrolled in person at CBH, and then screened to determine that they have GWI and objective evidence of a verbal retrieval impairment on neuropsychological testing.

3. If a subject scores > 2 SD below the mean on any of the following – the SORT clinical test, COWAT, BNT, and/or CAVLT, the subject will be enrolled in the treatment phase of the study and classified using the CDC criteria for subtype of Gulf War Illness.

4. Subjects will undergo a pre-treatment battery of detailed neuropsychological tests and EEG (SORT and Semantic Selection tasks with ERP). These will be used as outcome measures for the treatment trial.

5. We will enroll 80 subjects in treatment with one-half of the subjects receiving HD tDCS at 1 mA for 20 minutes over the preSMA region for 10 daily sessions; the other half of the subjects will initially receive sham HD tDCS and, after all follow-up evaluations are completed, they will receive active HD tDCS treatment. Participants will be randomly assigned to stimulation and sham conditions via algorithm.

6. Determine at 1 week, 3 months, and 6 months post-last-treatment whether the therapy has been effective by repeating the outcome measures (parallel versions when available) of the SORT, COWAT, BNT, CVLT, and ERP tasks.

B. Subject Recruitment

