Stage 1. Interview. We will phone screen approximately 120 Gulf War veterans (to obtain the targeted 80 subjects) with symptoms they attribute to service in the 1991 Persian Gulf War who have sought care at UT Southwestern Medical Center (Dr. [name]) or the Dallas VA Medical Center Neurology Clinic (Dr. [name]) for GWI. In addition, we have enrolled two large (>100 subjects enrolled after screening) veterans studies at the Center for BrainHealth using local advertisement and particularly our social networking public relations team. This team includes a combat veteran with extensive experience in using social media outlets to effectively recruit subjects for clinical trials.

The subjects will be screened initially by short telephone interview to determine whether they appear to have a Gulf War Illness, and will be briefly screened for exclusion criteria and the co-existing conditions listed below. The subjects will include men and women, ages 43 to 75 (ages 18 to 50 during the 1991 Gulf War) ofany race/ethnicity, and both enlisted and officer ranks. The potential subjects will then perform over the phone the Controlled Oral Word Association Test (COWAT) for three letters. Performance below 1 sd of the mean is the criterion, in our experience, to warrant further screening with more extensive testing for retrieval deficits (COWAT is a sensitive, brief measure of verbal retrieval). The telephone interview will be conducted

by a trained telephone interviewer. Those meeting the inclusion criteria will then be invited to participate in the second stage of the evaluation and be given an appointment for it.

Stage 2. Screening for a Retrieval Deficit. Those meeting the inclusion criteria will visit the UTD Center for BrainHealth for the study to be fully explained and formal consent obtained by study personnel. Once consent is obtained, the subject will be screened for a retrieval deficit with the neuropsychological tests of the Semantic Object Retrieval Test (SORT), COWAT (both letter and category fluency), Boston Naming Test (BNT), and the California Verbal Learning Test (CVLT). If a subject scores > 2 SD below the mean on any of these tests, the subject will be deemed to have a retrieval deficit and will be enrolled in the treatment phase of the study. These subjects will then be classified under the CDC criteria for GWI subtype and screened for co-morbid conditions/exclusion criteria that could potentially obfuscate the results of a treatment response.

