Stage 3. Pre-Treatment Testing. Those meeting criteria of having an established GWI and retrieval deficit will be scheduled for a neuropsychological test battery and EEG testing (SORT task with EEG, Semantic Selection task with EEG) as outlined under *Neuropsychological Measures and EEG Tasks* below. The two primary outcome measures will be the COWAT and CVLT. Secondary outcome measures will be SORT task behavioral and ERP measures, as well as Semantic Selection task performance and ERP measures.

Expected sample sizes. Our target sample of 80 Gulf War veterans who will complete the treatment phase of the study will afford us power to detect a statistically significant difference. Treatment-related change in verbal fluency and memory measures will be the primary outcome measures. Treatment-related change in verbal fluency and memory measures will be the primary outcome measures. A study of the effects of single-session tDCS applied to PFC on verbal fluency measures in normal controls showed a large effect-size, with standardized mean difference Cohen's d = 1.18.²⁰ Additionally, this treatment effect estimate on healthy controls is comparable to or exceeds the effect-size estimates for verbal fluency deficits in GWVs with GWI: Letter Fluency averaging over S1-3 Cohen's d = 0.69; S2 Cohen's d = 1.12, S3 Cohen's d = 0.85; Category Fluency averaging over S1-3 Cohen's d = 0.61, S2 Cohen's d = 0.81, S3 Cohen's d = .61.¹¹ For the treatment effect-size for S2, Cohen's $d = 1.18^{20}$, a sample size of 40 per group yields Power=0.92, and for the deficit effect-sizes for S2, Cohen's d = 1.12, and for S3 Cohen's d = .61, Power =0.94 and Power =0.89, respectively.

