The efficacy of HD tDCS will be assessed on each outcome. For the cognitive-behavioral measures (i.e., from SORT, COWA, BNT, CVLT, Trails A & B, Color Word Interference, Digits Forward & Backward, Rey-Osterrieth Complex Figures Test, Grooved Pegboard Test, and Beck Depression Inventory), a mixed-model MANOVA initially will be used to test for omnibus group (active vs sham) effects over time (i.e., Group X Time interaction effects). Given a significant multivariate effect, separate univariate mixed-model ANOVAs for each cognitive-behavioral measure will be evaluated for group (active vs sham) effects over time, and significant interaction effects will be followed up by separate pre- versus post-intervention evaluations for each tDCS group. Verbal fluency has been associated with sex, age, and education^{70, 71 but see 72}; thus, these variables will be included in the models. Additionally, potential mediating effects of IQ (based on NAART) and pre-test to post-test change in executive function, simple attention, working memory, processing speed, and depression (measured via Trails A & B, Color Word Interference, Digits Forward & Backward, Rey-Osterrieth Complex Figures Test, Grooved Pegboard Test, and Beck Depression Inventory) will be explored through covariate mediation modeling. For all testing, data will be thresholded for False Discovery Rates (FDR).

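### Power is based on 80 participants who complete treatment, but the plan enrols only 80 and makes no allowance for withdrawal

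*Combined protocol and SAP*

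**What the plan says.** Three places in the combined protocol and SAP give the target.

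- OBJECTIVES, Objective #5: "Enrollment of 80 participants is the target for enrollment in the active phase of the treatment trial".
- CLINICAL TRIAL, A. General Experimental Approach, item 5: "We will enroll 80 subjects in treatment with one-half of the subjects receiving HD tDCS at 1 mA for 20 minutes". The other half start on sham.
- CLINICAL TRIAL, B. Subject Recruitment, Stage 3, Expected sample sizes: "Our target sample of 80 Gulf War veterans who will complete the treatment phase of the study will afford us power". The same paragraph then states that "a sample size of 40 per group yields Power=0.92" at d = 1.18. It adds, for two deficit effect sizes, "for S2, Cohen's d = 1.12, and for S3 Cohen's d = .61, Power =0.94 and Power =0.89, respectively".

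Stage 1 of Subject Recruitment gives the screening pool: "We will phone screen approximately 120 Gulf War veterans (to obtain the targeted 80 subjects". That sentence does not say whether the 80 are enrolled or completing. Outcome tests follow at 1 week, 3 months and 6 months after the last session. The document states no withdrawal rate, no inflation of enrolment, no rule on replacing participants who withdraw, no analysis population, and no method for participants with missing outcome tests.

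**The concern.** The first two places count people entering treatment and the third counts people finishing it, yet all three give 80. Forty per group in the power statement is the whole of the 80, so it leaves no room for loss. A participant who stops during two weeks of sessions, or who misses the later tests, takes the trial below the size at which its power is quoted. Finishing the treatment phase may also mean only the 10 sessions. Loss between the last session and 6 months would then be a further shortfall that even a completer target does not cover.

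At stake is whether the stated sample size is what the design will deliver for the two primary outcomes, COWAT and CVLT, and whether staff have one unambiguous number at which enrolment stops.

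**Working it through.** **Inputs**

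- Enrolled in treatment: 80, so 40 per arm (Objective #5; General Experimental Approach, item 5).
- Completing: 80, so 40 per group (Expected sample sizes).
- Effect sizes and stated power (Expected sample sizes): d = 1.18, a single-session effect in normal controls, 0.92; d = 1.12, a deficit in syndrome group S2, 0.94; d = 0.61, a deficit in syndrome group S3, 0.89.
- Alpha and sidedness: not given for the power calculation. The Statistical Plan says only "For all testing, data will be thresholded for False Discovery Rates (FDR". Assumed here: 0.05, two-sided.
- Withdrawal w: not given. Assumed here: 10%, 15% or 20%, equal in both arms, with no outcome recovered from those lost.

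**Step 1. The plan's own figures.** Two-sample t-test with n = 40 per arm, noncentrality d × √(n/2) = d × √20 = d × 4.472.

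| d | noncentrality | stated power | two-sided 0.05 | one-sided 0.05 | two-sided 0.001 |
|---|---|---|---|---|---|
| 1.18 | 5.28 | 0.92 | 0.999 | above 0.999 | 0.96 |
| 1.12 | 5.01 | 0.94 | 0.999 | above 0.999 | 0.94 |
| 0.61 | 2.73 | 0.89 | 0.77 | 0.86 | 0.26 |

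No single alpha and sidedness tried (0.05 down to 0.001, one- and two-sided) reproduces all three. Only d = 1.12 is matched, at two-sided 0.001, where d = 0.61 falls to 0.26. The stated figures are also out of order: at the same n, d = 1.18 is given lower power than d = 1.12. This is a separate fault, but it means the stated figures cannot be scaled down for withdrawal. Power has to be recomputed.

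**Step 2. What 80 enrolled delivers.** Per arm, 40 × (1 − w); the standard error grows by 1/√(1 − w).

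- 10%: 36 per arm (72 in all), ratio 1.054, about 5% larger.
- 15%: 34 per arm (68), ratio 1.085, about 8% larger.
- 20%: 32 per arm (64), ratio 1.118, about 12% larger.

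**Step 3. Power at those numbers** (t-test, two-sided 0.05).

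| per arm | d = 0.61 | d = 1.12 | d = 1.18 |
|---|---|---|---|
| 40 | 0.77 | 0.999 | 0.999 |
| 36 | 0.72 | 0.997 | 0.999 |
| 34 | 0.70 | 0.995 | 0.998 |
| 32 | 0.67 | 0.993 | 0.996 |

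Hand check by normal approximation, Φ(d√(n/2) − 1.96), at d = 0.61 and n = 34: √17 = 4.123; 0.61 × 4.123 = 2.515; 2.515 − 1.96 = 0.555; Φ = 0.71, against 0.70 by the t-test.

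**Step 4. What 80 completers would need.** 80/(1 − w) = 88.9, 94.1 or 100, so 89, 95 or 100 enrolled. From 120 phone screens that is a yield of 74%, 79% or 83%, against the planned 80/120 = 67%. The two readings are therefore different recruitment plans.

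**The case against.** The strongest reply is that the Stage 3 sentence justifies power and is not a recruitment rule. On that view its reference to completion is loose drafting, and the enrolment target is plainly 80. That may well be the intent. It narrows the edit to one clause, but it does not rescue the 40 per group, which still assumes no loss.

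A second reply is that withdrawal hardly matters at the plan's own treatment effect. This stands: at d = 1.12 and 1.18, power stays at 0.99 or higher with 20% loss. The loss is material only at d = 0.61, which the plan itself offers as a basis for its sample size. Even there, the gap between the stated 0.89 and the recomputed 0.77 with nobody lost is larger than the further drop from 0.77 to 0.67 at 20% withdrawal.

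A reader might go further and infer that the plan will replace participants who withdraw until 80 finish, so that completion decides who counts. The documents do not support this. No section mentions replacement or a completer quota, and Stage 1 describes a single screening pool.

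A reader might also put a size on the resulting bias. If the 10% or 15% with the smallest gains vanish from the active arm alone, the arm means differ falsely by φ(z)/(1 − p) = 0.195 or 0.274 SD. That figure measures the effect of excluding non-completers and is the same with or without replacement. It assumes perfect selection in one arm and none in the other, and the plan nowhere says that non-completers are excluded. It should not be held against this plan.

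**Conclusion.** The inconsistency is real. Two sections count 80 in and the power paragraph counts 80 out, and these agree only with zero withdrawal. The consequence is a sample size statement that the design delivers only if nobody is lost. It does not show that the arm comparison is biased, or that the trial is underpowered for large effects.

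At 10% to 20% withdrawal the standard errors rise by 5% to 12%. Power at d = 0.61 goes from 0.77 to between 0.72 and 0.67, with no practical change at the two larger effects. These figures rest on assumed withdrawal rates, an assumed two-sided alpha of 0.05, and a simple two-arm comparison. The planned group-by-time analysis and the FDR threshold are not modelled. The wording conflict does not depend on any of these assumptions. It merits correction because the remedy is cheap and the figure is one on which the trial relies.

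**What to change.** 1. In Expected sample sizes, replace the clause that describes the 80 as completers with: randomised (40 per arm). This matches Objective #5 and item 5 of the General Experimental Approach.
2. State an assumed withdrawal allowance covering both the sessions and follow-up to 6 months. Give the expected number assessed per arm (for example 34 at 15%).
3. Recompute power at that number, with alpha and sidedness stated. Do not start from 0.92, 0.94 and 0.89.
4. State in the Statistical Plan that all randomised participants, including those who stop sessions early, are invited to the 1-week, 3-month and 6-month tests already scheduled and are analysed in their assigned arm.

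The cost is wording, and a less favourable stated power at d = 0.61. No extra patients are needed, and early stoppers would attend only visits already planned for everyone. If the sponsor prefers to keep 40 assessed per arm, enrolling 89 to 100 is an equally valid choice. The target and the screening yield would then have to be changed throughout.

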b. Controlled Oral Word Association Test (COWAT).⁴⁰ This is an assessment of word retrieval during which the patient is required to produce as many words in one minute that begin with either a specific letter (e.g., *F*, *A*, or *S*) or members of a specific category (e.g., *animals*, *fruit and vegetables*). Psychometrics: Cronbach's alpha = .83 for the number of items generated per condition; test-retest reliability r = .74; test-retest also has shown significant gains observed from first (*M*=39.7, *SD*=10.48) to second (*M*=42.5, *SD*=9.9) administration, t(1, 119)=4.19, p<.001.⁴¹

c. Boston Naming Test (BNT).⁴² The test consists of 60 pictures of items where each is presented one at a time for the patient to provide the name of the item depicted. The task will be split into two equivalent 30 item tests (Cronbach alpha = .88; whole sample agreement between forms kappa = .93; Graves et al., 2004). The test assesses visuoperceptual processing, access to semantic knowledge and access to and production of the name of the object, which marked word retrieval from a visual input. Internal consistency ranges from r = .78 to .96 across studies. Test–retest stability in cognitively normal adults varies as a function of time interval and sample composition and ranges from r = .59 to .92.⁴³

d. California Verbal Learning Test (CVLT-II).⁴⁴ The test is a list-learning task where the tester reads aloud a list, called "Monday's shopping list." The list contains sixteen common words, each of which belongs to one of four categories. The tester records how many items the patient remembers over several repeated trials and if the patient is making use of category information. There is also a delayed recall trial after 20 minutes. The test is an indirect measure of word retrieval in that successful word retrieval from semantic memory is needed to perform well in this episodic memory task. The CVLT-II has generally large test-retest correlation coefficients for the primary CVLT-II measures in both the standard/standard (range r = 0.80-0.84) and standard/alternate (range r = 0.61-0.73) cohorts, with reliability coefficients for primary measures ranging from 0.80 (e.g., total trials 1–5) to 0.84 (recognition discriminability).⁴⁵

Parallel versions are available for all of the above neuropsychological tests. Additional neuropsychological measures included will be (organized by domain of cognitive function):

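### The three power values given for 40 per group contradict each other and cannot come from any one test

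*Combined protocol and SAP*

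**What the plan says.** All the power figures are in section B (Subject Recruitment), under Expected sample sizes. For d = 1.18 the text says that "a sample size of 40 per group yields Power=0.92, and for the deficit effect-sizes for S2" (d = 1.12) and S3 (d = 0.61) the values are "Power =0.94 and Power =0.89, respectively". One sample size is given for all three. No test, alpha, sidedness or repeated-measures correlation is given.

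The d = 1.18 is introduced with the words "For the treatment effect-size for S2". Earlier in the same paragraph its source is described as "A study of the effects of single-session tDCS applied to PFC on verbal fluency measures in normal controls". The list of deficit sizes puts S2's 1.12 under letter fluency and S3's 0.61 under category fluency.

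The paragraph speaks of "Our target sample of 80 Gulf War veterans who will complete the treatment phase of the study". Objective #5 says "Enrollment of 80 participants is the target for enrollment in the active phase of the treatment trial", and item 5 of the General Experimental Approach says "We will enroll 80 subjects in treatment".

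Elsewhere, the Statistical Plan describes an omnibus mixed-model MANOVA for Group by Time, followed by univariate mixed-model ANOVAs, with false discovery rate control. Section C gives the COWAT "test-retest reliability r = .74". Neither is tied to the power figures.

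**The concern.** The largest effect is given less power than the next largest at the same sample size, which is impossible under one method. Power also drops only from 0.94 to 0.89 while d falls by almost half, from 1.12 to 0.61.

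This paragraph is the only quantitative support for 80 veterans. The value that matters most is the one for d = 0.61, the smallest effect used in the power sentence, and a reader cannot tell which analysis stands behind it.

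**Working it through.** **Inputs.** From Expected sample sizes: 40 per group; d = 1.18, 1.12 and 0.61; stated power 0.92, 0.94 and 0.89. From section C: COWAT test-retest r = 0.74. Assumed, because the paragraph is silent: two-sided alpha 0.05, and r = 0.5 as a low value, since a group selected for a deficit of more than 2 SD may correlate less well than a general sample.

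**1. Trying to reproduce the plan's figures.** Two-sample t-test, noncentrality d × √(n/2) = d × √20, 78 degrees of freedom, two-sided 5% critical value 1.991.

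| d | noncentrality | power, two-sided 0.05 | power, one-sided 0.05 | stated |
|---|---|---|---|---|
| 1.18 | 5.28 | 0.9994 | 0.9998 | 0.92 |
| 1.12 | 5.01 | 0.9986 | 0.9995 | 0.94 |
| 0.61 | 2.73 | 0.769 | 0.855 | 0.89 |

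None is reproduced. Isolated matches exist. For example, two-sided alpha 0.001 gives 0.939 at d = 1.12, but it then gives 0.964 at 1.18 and 0.26 at 0.61. To obtain the stated values one by one at two-sided 0.05, the t-test would need about 18, 21 and 56 per group.

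**2. Could any single method give all three?** Write power = Φ(k·d − 1.96), where k absorbs sample size and correlation. Fix k from one stated value and read off the others.

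| Fitted to | k | power at 1.18 | at 1.12 | at 0.61 |
|---|---|---|---|---|
| 0.94 at 1.12 | (1.555 + 1.960)/1.12 = 3.138 | 0.959 | 0.94 | 0.48 |
| 0.92 at 1.18 | (1.405 + 1.960)/1.18 = 2.852 | 0.92 | 0.891 | 0.41 |
| 0.89 at 0.61 | (1.227 + 1.960)/0.61 = 5.224 | above 0.999 | above 0.999 | 0.89 |

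Letting alpha vary does not help. The pair 0.94 and 0.89 needs a one-sided alpha of about 0.80, and the pair 0.92 and 0.89 about 0.85.

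**3. Would a repeated-measures correlation explain it?** For a change score, replace d by d/√(2(1 − r)). For a baseline-adjusted comparison, replace d by d/√(1 − r²) and lose one degree of freedom.

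| Analysis, two-sided 0.05, 40 per group | d = 0.61, r = 0.5 | d = 0.61, r = 0.74 | d = 1.12 and 1.18 |
|---|---|---|---|
| Change score | 0.61/1.000 = 0.61, power 0.769 | 0.61/0.721 = 0.846, power 0.962 | above 0.998 |
| Baseline-adjusted | 0.61/0.866 = 0.704, power 0.875 | 0.61/0.673 = 0.907, power 0.980 | above 0.999 |

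The 0.89 alone is reached at r = 0.64 (change) or r = 0.53 (adjusted). The same correlations move the other two values further above 0.92 and 0.94.

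**4. Sensitivity for d = 0.61.** If alpha were 0.025 for each of the two primary outcomes (assumption), the change score gives 0.67 at r = 0.5 and 0.93 at r = 0.74. If 80 are enrolled and 15% are lost (assumption; 40 × 0.85 = 34 per group), power runs from 0.70 (plain t-test) to 0.96 (adjusted, r = 0.74).

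**The case against.** The best defence is that the analysis uses repeated measures, so plain t-test values are the wrong yardstick. With the documents' own COWAT correlation of 0.74, a change score gives 0.96 for d = 0.61, above the stated 0.89. That stands as an argument against calling the trial underpowered. It does not rescue the paragraph, because no correlation can put 0.92 at d = 1.18 beside 0.94 at d = 1.12.

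A second objection is that none of the analyses computed here is the planned one. The Statistical Plan has a MANOVA gate, three covariates, several follow-ups and false discovery rate control, and it names no baseline covariate. This is fair. The values above are reference points, and the claim that 0.92 and 0.94 are too low holds for these analyses, not for every possible alpha. Without the baseline-adjusted analysis, the best case for d = 0.61 is 0.96 rather than 0.98.

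Third, the label and enrolment points are not arithmetic, and the sentence listing the deficit sizes lets a careful reader work out which fluency measure each d belongs to. That is true. They are included because the same paragraph has to be rewritten. Hypothesis #2a does predict recovery to premorbid levels, so using deficit sizes as treatment effects is not baseless, but the paragraph does not state that assumption.

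**Conclusion.** The concern holds. The order of 0.92 and 0.94 is impossible under any common test and alpha, whatever those are, and this conclusion needs no assumption. No single setting tried reproduces all three values.

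The size of the error depends on assumptions that the paragraph should have supplied. At two-sided 0.05 with 40 completers per group, power for the two large effects is above 0.998. For d = 0.61 it is 0.77 with a plain t-test, 0.77 to 0.96 with a change score, and 0.88 to 0.98 with baseline adjustment (r from 0.5 to 0.74). The chance of missing such an effect could be about 23% or about 2% (about 4% at best with a change score). The errors do not all favour the trial.

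The labels are also wrong or incomplete: the d = 1.18 attributed to S2 comes from normal controls after one session. Whether 80 is the number enrolled or the number completing is inconsistent, and no loss allowance is stated. This should be corrected, but it is a fault in the justification and not evidence that the design fails.

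**What to change.** Delete the three values and recompute them from one named test, stating alpha, sidedness, completers per group and, if the basis is repeated measures, the correlation. Say how the MANOVA gate and the false discovery rate control enter, or that the calculation leaves them out. Give a range for d = 0.61.

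If the Group by Time change is the basis, wording could be:

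> With 40 completers per group and a two-sided 0.05 test of pre-to-post change, before any multiplicity adjustment, power for d = 0.61 is 0.77 if the pre-post correlation is 0.5 and 0.96 if it is 0.74. For d = 1.12 and d = 1.18 it exceeds 0.99.

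For reference, a plain two-sided 0.05 t-test at 40 per group detects d = 0.63 with 80% power and d = 0.73 with 90% power.

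In the same paragraph:
- Remove the S2 label from d = 1.18.
- Name letter or category fluency beside each deficit size.
- State that using deficit sizes as treatment effects assumes full recovery relative to sham.
- Reconcile 80 enrolled (Objective #5 and General Experimental Approach, item 5) with 80 completing, and give power at the resulting number of completers.

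The cost is one rewritten paragraph, with matching wording on the number 80 where it recurs. No extra patients and no change to conduct or analysis are needed. The figure for d = 0.61 may become less favourable; the other two become more favourable on the analyses shown.
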